3.3.3 Benefits/Risks for the Combination of Pembrolizumab and Epacadostat

The combination of pembrolizumab and epacadostat has the potential to cause more frequent, more severe, and/or new immune-related toxicities as compared with each agent individually.

Study INCB 24360-202 (KEYNOTE-037) is an ongoing Phase 1/2 study of epacadostat administered in combination with pembrolizumab, with Phase 1 being a dose-escalation phase and Phase 2 being an open-label, single arm, cohort expansion phase. Phase 1 is being conducted in participants with advanced or metastatic solid tumors including Stage 3B, Stage IV, or recurrent NSCLC, melanoma, TCC of the genitourinary tract, renal cell cancer, triple negative breast cancer, adenocarcinoma of the endometrium, or SCCHN who have disease progression on at least 1 line of therapy for advanced or metastatic cancer (except melanoma). Phase 2 is conducted in participants with NSCLC, melanoma, transitional cell carcinoma of the genitourinary tract, triple negative breast cancer, SCCHN, ovarian cancer, diffuse large B-Cell lymphoma, clear cell renal cell cancer, gastric cancer, hepatocellular carcinoma, and microsatellite instability (MSI) high colorectal cancer.

Safety data is available on 294 participants from Phase 2 treated with the recommended Phase 2 dose of epacadostat 100 mg BID and pembrolizumab 200 mg Q3W [Hamid, O., et al 2017]. The most frequently reported ($\geq 10\%$) TRAEs of any grade were fatigue (29%), rash (17%), nausea (11%), and pruritus (10%). Rash includes the preferred terms rash, rash generalized, rash macular, rash maculopapular, and rash pruritic. TRAEs Grade ≥ 3 were observed in 18% of participants. The most common TRAEs Grade ≥ 3 were increased lipase (4%) and rash (3%). There was one treatment-related death due to respiratory failure which was secondary to aspiration pneumonia.

Additional details regarding specific benefits and risks for participants participating in this clinical trial may be found in Section 3.2.1.4 and the accompanying IB and Informed Consent documents.

4. Objectives/Hypotheses and Endpoints

NOTE: As of Amendment 04, the primary endpoint of the study will be ORR based on RECIST 1.1 as assessed by the investigator. All other efficacy endpoints, including imaging, will no longer be collected or performed after the first imaging assessment at Week 9. This section has been updated accordingly.

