Rash	Grade 1 or 2	Pembrolizumab	Continue	
 Manage with topical steroids with or without drug interruption. 	
 If toxicity does not resolve within 12 weeks of last dose, or cannot taper below 10 mg or less of prednisone or equivalent within 12 weeks, must permanently discontinue. Restart epacadostat at same dose if rash is mild and assessed as Grade 3 based only on body surface area and resolves without oral steroids. If oral steroids are required, or rash is severe, decrease by 1 dose level once resolved to Grade 0-1.
		Epacadostat or matching placebo	Continue		
	Grade 3 ^c	Pembrolizumab	Withhold until Grade 0-1	
 Administer corticosteroids (initial dose of 1-2 mg/kg prednisone or equivalent) followed by taper. 	
		Epacadostat or matching placebo	Withhold until Grade 0-1 Once resolved to Grade 0-1, may restart: Related: Reduce by 1 dose level. Not Related: Same dose level.		

Immune-related AEs	Toxicity Grade or Conditions (CTCAEv4.0)	Study Medication	Action Taken with Study Medication	irAE Management with Corticosteroid and/or Other Therapies	Monitor and Follow-up
	Grade 4	Pembrolizumab	Permanently discontinue	
 Administer corticosteroids (initial dose of 1-2 mg/kg prednisone or equivalent) followed by taper. 	
		Epacadostat or matching placebo	Permanently discontinue		
Asymptomatic Amylase or Lipase Increased	Grade 3	Pembrolizumab	May continue treatment with MSD Clinical Director approval		
 Permanently discontinue if clinical signs and symptoms of pancreatitis develop (abdominal pain, nausea, vomiting). If toxicity does not resolve within 12 weeks of last dose after an interruption, must permanently discontinue unless approved by the medical monitor to continue. If Grade 4 lipase/amylase elevation is asymptomatic and abdominal imaging suggests no pathology, study drug administration dosing may continue (with or without dose reduction) with medical monitor approval.
		Epacadostat or matching placebo	May continue treatment with MSD Clinical Director approval		
	Grade 4	Pembrolizumab	Withhold until toxicity resolves to Grade 0-1		
		Epacadostat or matching placebo	Withhold until toxicity resolves to Grade 0-1 Once resolved to Grade 0-1, may restart: Related: Reduce by 1 dose level. Not Related: Same dose level.		

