
General Instructions:
 
 1. Corticosteroid taper should be initiated upon AE improving to Grade 1 or less and continue to taper over at least 4 weeks. 2. For situations where pembrolizumab and epacadostat/placebo have been withheld, pembrolizumab and epacadostat/placebo can be resumed after AE has been reduced to Grade 1 or 0 and corticosteroid has been tapered. Pembrolizumab and epacadostat/placebo should be permanently discontinued if AE does not resolve within 12 weeks of last dose or corticosteroids cannot be reduced to ≤ 10 mg prednisone or equivalent per day within 12 weeks. 3. For severe and life-threatening irAEs, IV corticosteroid should be initiated first followed by oral steroid. Other immunosuppressive treatment should be initiated if irAEs cannot be controlled by corticosteroids. 4. If the same AE that required epacadostat dose reductions to dose level -2 re-occurs, regardless of the causality to epacadostat, epacadostat should be discontinued. If a participant who is being treated at dose level -2 has a different Grade ≥ 3 AE that is considered unrelated to epacadostat by the investigator, the participant may resume study treatment at dose level -2 after discussion with the study medical monitor. 
NOTES:
 
 a. For participants with Grade 3 or 4 immune-related endocrinopathy where withholding of pembrolizumab and epacadostat/placebo is required, pembrolizumab and epacadostat/placebo may be resumed when AE resolves to \leq Grade 2 and is controlled with hormonal replacement therapy or achieved metabolic control (in case of T1DM) b. Withhold OR permanently discontinue pembrolizumab + epacadostat/placebo at the discretion of the Investigator. c. Participants with Grade 3 rash in the absence of desquamation, no mucosal involvement, does not require systemic steroids, and resolves to Grade 1 within 14 days does not have to hold study medication 
Abbreviations: AEs = adverse events; ALT (SGPT) = alanine aminotransferase (serum glutamic pyruvic transaminase); AST (SGOT) = aspartate aminotransferase (serum glutamic oxaloacetic transaminase); CTCAE = Common Terminology Criteria for Adverse Events; IV = intravenous; irAE = infusion-related adverse events; T1DM = Type 1 diabetes mellitus
					

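### Table 3 sets the epacadostat restart dose after Grade 3 rash by two unreconciled rules, so one rash profile is told both to reduce and to restart at the same dose

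*Combined protocol and SAP*

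**What the plan says.** Four places in Section 7.2.1, Table 3, bear on a Grade 3 rash.

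- **Action column.** Both drugs are withheld until Grade 0-1. For epacadostat or placebo it continues: "Once resolved to Grade 0-1, may restart: Related: Reduce by 1 dose level. Not Related: Same dose level".
- **Monitoring column.** "Restart epacadostat at same dose if rash is mild and assessed as Grade 3 based only on body surface area", provided that it clears without oral steroids. The next sentence calls for a one-level decrease when oral steroids were needed or the rash was severe. Causality is not mentioned.
- **Steroid column.** Corticosteroids, starting at 1-2 mg/kg prednisone or equivalent and then tapered, with no condition attached.
- **Note c**, marked on the Grade 3 label. A participant whose rash has no desquamation or mucosal involvement, needs no systemic steroids and "resolves to Grade 1 within 14 days does not have to hold study medication".

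Neither the table, its general instructions nor the surrounding text says which of these governs. The text around Tables 3 and 4 bars any return to a higher epacadostat dose after a reduction. Table 4 gives the steps as 100, 50 and 25 mg BID. The Second Course schedule (Section 2.2) and Section 7.2.2 carry the last epacadostat dose level into retreatment.

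**The concern.** Two cells of one row answer the same question, the epacadostat dose at restart, with different criteria. Where the criteria point in different directions, the site has no basis for choosing. Because a reduction is permanent, that choice can set the dose for the rest of the initial phase and for any Second Course. It also uses one of only two reduction steps: under general instruction 4, epacadostat is discontinued if the event that led to level -2 recurs there. Dose differences between participants would then partly reflect how a site reads the table. Treatment continues after Amendment 04 for participants judged to benefit, so the table is still in use.

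**Working it through.** No figure in the plan depends on this row, so the check applies the texts side by side. I read relatedness in the epacadostat cell as relatedness to epacadostat or placebo. The table does not say so.

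| Grade 3 rash | Action column | Monitoring column |
|---|---|---|
| Related; mild, surface area only; no oral steroids | Reduce | **Same dose** |
| Related; oral steroids needed, or severe | Reduce | Reduce |
| Pembrolizumab only; mild, surface area only; no oral steroids | Same dose | Same dose |
| Pembrolizumab only; oral steroids needed, or severe | Same dose | **Reduce** |

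The first row is the main conflict and the fourth is its reverse.

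**How widely the rules diverge.** Take five yes/no features: related; mild and surface-area-only; steroids; desquamation or mucosal involvement; Grade 1 within 14 days. That gives 2^5 = 32 profiles. Dropping mild, surface-area-only rash with desquamation or mucosal involvement removes 8, leaving 24. Reading every rash that is not mild as severe, the columns disagree in 12:

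- 2 related profiles (mild, surface-area-only, no steroids; the 14-day feature either way).
- 10 profiles not related to epacadostat: 6 with steroids, and 4 without that depend on reading not mild as severe.

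These are counts of profiles, not of participants. One of the 2 related profiles also meets note c. That profile can be held or dosed through and, if held, restarted at the same dose or reduced.

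**Steroid column and note c.** The same-dose rule presupposes no oral steroids and note c no systemic steroids, yet the steroid cell prescribes corticosteroids for every Grade 3 rash. Note c also lifts the hold on the strength of a 14-day outcome that is unknown when the hold is decided.

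**Size.** Section 3.3.3 reports Grade 3 or higher treatment-related rash in 3% of 294 participants at 100 mg BID with pembrolizumab 200 mg Q3W. Section 10.9 plans about 50 per arm. Expected in the combination arm: 50 × 0.03 = 1.5. This is an upper bound on conflicting cases there, since it includes Grade 4 rash (permanently discontinued, no conflict) and Grade 3 rash on which the columns agree. The documents give no rate for the conflicting profile. One step down from the starting dose halves it (100 to 50 mg BID).

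**The case against.** The best reply is that the action wording is a stock phrase repeated in most rows of Table 3, while the monitoring text is specific to rash and can be read as refining it. That reading is coherent, but the table does not state it. It would also let the monitoring column override the same-dose rule for unrelated rash. Two careful sites could still differ.

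Other replies narrow the point:

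- Section 7.7.4 releases the investigator from the guidance when an event is related to neither drug, and Appendix 4 says causality should generally be assigned to the whole regimen. The reverse conflict is therefore limited to rash attributed to pembrolizumab alone. The same default makes related the usual attribution, so the main conflict is untouched.
- Section 7.7.4 describes the steroid measures as suggested and for use where appropriate. The unconditional steroid cell is therefore only supporting evidence.
- Note c is a marked, permissive exception to the hold. It does not contradict the action column. Its fault is the condition known only later.

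A reader might also infer that the Grade 4 asymptomatic amylase/lipase row gives opposite orders. Its action column says "Withhold until toxicity resolves to Grade 0-1", while its monitoring column says "study drug administration dosing may continue (with or without dose reduction) with medical monitor approval". The documents do not support that inference: continuation also requires abdominal imaging that shows no pathology. This is a default with a conditional exception, so participants who are held and participants who continue are not alike. The action column does not mention the exception, and the table gives no criterion for choosing between continuing with and without a reduction. The approvers named for Grade 3 and Grade 4 serve different decisions.

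**Conclusion.** The Grade 3 rash row contradicts itself on the epacadostat restart dose for a drug-related, mild, surface-area-only rash that clears without oral steroids. The reverse conflict can arise for a rash attributed to pembrolizumab alone that needs oral steroids. The main conflict rests on the wording alone. The size rests on the 3% rate carrying over to this population: at most about 1.5 expected among 50 combination participants, with the conflicting share unknown. Placebo-arm participants fall under the same row while blinded, but the documents give no Grade 3 rash rate for pembrolizumab alone.

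Three stronger readings should be resisted.

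- **Frequency.** The 3% rate gives a 1 − 0.97^50 = 0.78 chance of at least one Grade 3 or higher rash among 50. That is not the chance of a conflict, because it counts events on which the columns agree.
- **Efficacy.** ORR is estimated descriptively by randomized arm with no hypothesis test, so its analysis and the precision in Table 12 do not change. Enrollment stopped on 02-MAY-2018 and Amendment 04 was approved on 15 June 2018. If the last randomization was near the stop date, the last Week 9 scan falls 63 days later, about 4 July (±7 days). A later wording change could hardly alter dosing before that scan; it matters for continuing treatment.
- **Safety tables.** Table 11 has no dose-reduction category, and the restart dose does not change whether an interruption is counted. Only uncertainty over the hold, through note c, bears on that count.

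**What to change.** Reconcile the action, steroid and monitoring columns of the Grade 3 rash row with note c so that together they give one consistent instruction on the hold and on the epacadostat restart dose. The sponsor decides which clinical rule stands; nothing here favors either. As a minor clarification, cross-reference the imaging-and-approval exception in the action column of the Grade 4 amylase/lipase row.

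The cost is table wording, through a clarification letter or the next amendment. No new procedures or data are needed.

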7.2.1.1 Procedures for Participants Exhibiting Serotonin Syndrome (SS)

There is a rare chance that epacadostat could cause an increase in serotonin levels in the brain that might trigger SS [Boyer EW, Shannon M 2005], when administered in combination with other serotonergic agents. This syndrome has been most closely associated with use of MAOIs, meperidine, linezolid, or methylene blue; all of these agents are prohibited during the study.

Selective serotonin reuptake inhibitors (SSRIs) and serotonin/norepinephrine reuptake inhibitors (SNRIs) are permitted in the study. Serotonin syndrome usually manifests with autonomic changes, mental status changes, and neurological findings. These mild, moderate, and severe signs and symptoms of SS (summarized in Table 5) should be evaluated in the context of possible comorbid conditions as well.

The following procedures will be implemented if participants exhibit the signs/symptoms of SS (described in Table 5), including tremor; hyperreflexia; spontaneous, ocular, or inducible clonus; together with agitation, fever, diaphoresis, or muscle rigidity.

- Immediately interrupt study treatment administration.
- Immediately interrupt any SSRI or SNRI administration.
- Provide appropriate medical management of the participant until all signs/symptoms are resolved (eg, IV fluids and/or sympathomimetic amines for hypotension, benzodiazepines for agitation, administration of 5-hydroxytryptamine antagonists such as cyproheptadine).
- If etiologies other than SS are excluded, pembrolizumab administration may be resumed unless other AE management guidelines apply for the specific event.
- If participant chooses to remain in the study, restart study treatment after the SSRI or SNRI has been discontinued, no sooner than after 5 half-lives have elapsed for the specific SSRI or SNRI in question, and after resolution of signs/symptoms of SS. The SSRI or SNRI dosing MAY NOT be restarted.

- If participant chooses to withdraw from the study, or must restart treatment with SSRI or SNRI, the participant should be scheduled for a follow-up visit. Treatment with SSRI or SNRI may be initiated 2 weeks after resolution of signs and symptoms of SS.
- If a participant had experienced moderate or severe unconfounded SS in the opinion of the investigator, without concomitant SSRI or SNRI usage, or serotonergic concomitant medications, only pembrolizumab administration may be resumed; epacadostat/placebo treatment should be permanently discontinued.

Table 5 Signs and Symptoms of Serotonin Syndrome

Seriousness	Autonomic signs	Neurological signs	Mental status	Other
Mild	Afebrile or low-grade fever Tachycardia Mydriasis Diaphoresis or shivering	Intermittent tremor Akathisia Myoclonus Mild hyperreflexia	Restlessness Anxiety	
Moderate	Increased Tachycardia Fever (up to 41 C) Diarrhea with hyperactive bowel sounds Diaphoresis with normal skin color	Hyperreflexia Inducible clonus Ocular clonus (slow continuous lateral eye movements) Myoclonus	Easily startled Increased confusion Agitation and hypervigilance	Rhabdomyolysis Metabolic acidosis Renal Failure Disseminated intravascular coagulopathy (secondary to hyperthermia)
Severe	Temperature often more than 41 C (Secondary to increased tone)	Increased muscle tone (lower limb > upper) Spontaneous clonus Substantial myoclonus or hyperreflexia	Delirium Coma	As above

Source: [Boyer, E. W. 2005]

7.2.1.2 Dose Modification and Toxicity Management of Infusion-reactions Related to Pembrolizumab

Pembrolizumab may cause severe or life threatening infusion-reactions including severe hypersensitivity or anaphylaxis. Signs and symptoms usually develop during or shortly after drug infusion and generally resolve completely within 24 hours of completion of infusion. Dose modification and toxicity management guidelines on pembrolizumab associated infusion reaction are provided in [Table 6](#).

Table 6 Pembrolizumab Infusion Reaction Dose Modification and Treatment Guidelines

NCI CTCAE Grade	Treatment	Premedication at Subsequent Dosing

Grade 1 Mild reaction; infusion interruption not indicated; intervention not indicated
	
Increase monitoring of vital signs as medically indicated until the participant is deemed medically stable in the opinion of the investigator.
	
None

Grade 2 Requires therapy or infusion interruption but responds promptly to symptomatic treatment (eg, antihistamines, NSAIDs, narcotics, IV fluids); prophylactic medications indicated for ≤ 24 hrs
	
Stop Infusion. Additional appropriate medical therapy may include but is not limited to: IV fluids Antihistamines NSAIDs Acetaminophen Narcotics
 
Increase monitoring of vital signs as medically indicated until the participant is deemed medically stable in the opinion of the investigator.
 
If symptoms resolve within 1 hour of stopping drug infusion, the infusion may be restarted at 50% of the original infusion rate (eg from 100 mL/hr to 50 mL/hr). Otherwise dosing will be held until symptoms resolve and the participant should be premedicated for the next scheduled dose.
 
Participants who develop Grade 2 toxicity despite adequate premedication should be permanently discontinued from further study drug treatment
	
Participant may be premedicated 1.5 h (\pm 30 minutes) prior to infusion of pembrolizumab with: Diphenhydramine 50 mg po (or equivalent dose of antihistamine). Acetaminophen 500-1000 mg po (or equivalent dose of analgesic).

NCI CTCAE Grade	Treatment	Premedication at Subsequent Dosing

Grades 3 or 4
 
Grade 3: Prolonged (i.e., not rapidly responsive to symptomatic medication and/or brief interruption of infusion); recurrence of symptoms following initial improvement; hospitalization indicated for other clinical sequelae (eg, renal impairment, pulmonary infiltrates)
 
Grade 4: Life-threatening; pressor or ventilatory support indicated
	
Stop Infusion.
 
Additional appropriate medical therapy may include but is not limited to:
 
Epinephrine** IV fluids Antihistamines NSAIDs Acetaminophen Narcotics Oxygen Pressors Corticosteroids
 
Increase monitoring of vital signs as medically indicated until the participant is deemed medically stable in the opinion of the investigator.
 
Hospitalization may be indicated.
 
**In cases of anaphylaxis, epinephrine should be used immediately.
 
Participant is permanently discontinued from further study drug treatment.
	
No subsequent dosing

Appropriate resuscitation equipment should be available at the bedside and a physician readily available during the period of drug administration. For further information, please refer to the Common Terminology Criteria for Adverse Events v4.0 (CTCAE) at http://ctep.cancer.gov. CTCAE=Common Terminology Criteria for Adverse Events; IV=intravenous; NCI=National Cancer Institute; NSAIDs=nonsteroidal anti-inflammatory drugs; PO=oral.
		

7.2.1.3 Interruptions Unrelated to Adverse Events

Dosing interruptions are permitted for situations other than treatment-related AEs, such as in the case of medical/surgical events or logistical reasons not related to study treatment (eg, elective surgery, unrelated medical events, participant vacation, or holidays). Participants should be placed back on study treatment within 3 weeks of the scheduled interruption, unless otherwise discussed with MSD. The reason for interruption should be documented in the participant's study record.

7.2.2 Second Course Phase (Retreatment)

NOTE: As of Amendment 04, disease assessment will be performed by the investigator per local SoC guidelines; placebo will not be administered after unblinding. This section has been updated accordingly.

All participants who stop study treatment with SD or better may be eligible for up to an additional 17 cycles (approximately 1 year) of combination treatment of pembrolizumab plus epacadostat or pembrolizumab monotherapy if they progress after stopping trial treatment from the initial treatment phase. This retreatment is termed the Second Course Phase of this trial and is only available if the trial remains open and the participant meets the following conditions:

Either

- Stopped initial treatment with trial treatment after attaining CR evaluated by the local investigator based on RECIST 1.1, and
 - Was treated with at least 8 cycles of trial treatment before discontinuing treatment, and
 - Received at least 2 treatments with pembrolizumab beyond the date when the initial CR was declared

OR

- Had SD, PR, or CR and stopped trial treatment after completion of 35 cycles (approximately 2 years) of trial treatment

AND

- Experienced radiographic disease progression verified by investigator assessment based on RECIST 1.1 after stopping initial treatment, and
 - No new anticancer treatment was administered after the last dose of trial treatment, and
 - The participant meets all of the safety parameters listed in the inclusion criteria and none of the safety parameters listed in the exclusion criteria, and
 - The trial is ongoing.

Participants who enter the Second Course Phase will be retreated with the same combination and epacadostat dose level as when they last received the combination of pembrolizumab plus epacadostat or pembrolizumab monotherapy in the initial treatment phase, unless a study-wide decision is otherwise announced by the DMC or Sponsor via an administrative memo. Note: If epacadostat was discontinued it should not be restarted. Treatment will be administered for up to an additional 17 cycles (approximately 1 year) using the Second Course Phase SoA in Section 2.2.

An objective response or disease progression that occurs during the Second Course Phase for a participant will not be counted as an event for the primary analysis of this study.

